7.2. Participant Discontinuation/Withdrawal from the Study

Discontinuation is expected to be uncommon.

A participant may withdraw from the study:

- at any time at the participant's own request
- at the request of the participant's designee
- at the discretion of the investigator for safety, behavioral, compliance, or administrative reasons
- if enrolled in any other clinical study involving an investigational product, or enrolled in any other type of medical research judged not to be scientifically or medically compatible with this study
- if the participant, for any reason, requires treatment with a therapeutic agent that is prohibited by the protocol and has been demonstrated to be effective for treatment of the study indication. In this case, discontinuation from the study occurs prior to introduction of the new agent.

At the time of discontinuing from the study, if possible, the participant will complete procedures for an ED visit as shown in the SoA. If the participant has not already discontinued the study intervention, the participant will be permanently discontinued from the study intervention at the time of the decision to discontinue the study.

If the participant withdraws consent for disclosure of future information, the sponsor may retain and continue to use any data collected before such a withdrawal of consent. If a participant withdraws from the study, the participant may request destruction of any samples taken and not tested, and the investigator must document this in the site study records.

7.3. Lost to Follow up

A participant will be considered lost to follow-up if he or she repeatedly fails to return for scheduled visits and is unable to be contacted by the study site. Site personnel or designee are expected to make diligent attempts to contact participants who fail to return for a scheduled visit or were otherwise unable to be followed up by the site.

8. Study Assessments and Procedures

Study procedures and their timing are summarized in the SoA.

Immediate safety concerns should be discussed with the sponsor immediately upon occurrence or awareness to determine if the participant should continue or discontinue study intervention.

Adherence to the study design requirements, including those specified in the SoA, is essential and required for study conduct.

All screening evaluations must be completed and reviewed to confirm that potential participants meet all eligibility criteria. The investigator will maintain a screening log to record details of all participants screened and to confirm eligibility or record reasons for screening failure, as applicable.

Joint and safety assessors

To prevent potential bias from observed efficacy or laboratory changes, a "dual assessor" approach will be used to evaluate efficacy and safety.

The same assessor should perform the joint assessments of a participant, whenever possible, throughout the study to minimize interobserver variation.

A back-up independent joint assessor should be identified.

The independent joint assessors should be a CC Any other joint assessor must be trained and competent in performing such assessments.

8.1. Efficacy Assessments

Order of assessments

[figure not shown]
The patient-reported and clinician-reported efficacy assessments should be completed in the following order

[figure not shown]

Additional calculations and assessments

Efficacy measurements also include calculations and assessments by

8.1.8. Clinician Administered Tender or Swollen Joint Count (TSJC) (68/66)

The clinician administered TSJC (68/66) will be performed at visits according to the SoA.

Data will be captured on an electronic tablet collected at site visits.

The same assessor should perform the joint assessments of a participant, whenever possible, throughout the study to minimize interobserver variation.

Tender Joint Counts

The number of tender joints will be determined by examination of 68 joints, 34 joints on each side of the participant's body.

The 68 joints to be assessed and classified as tender or not tender include

- 2 temporomandibular joints
- 2 acromioclavicular joints
- 2 elbow joints
- 2 hip joints
- 2 ankle joints
- hands
 - o 10 metacarpophalangeal joints
 - o 2 interphalangeal joints of the thumb
 - 8 proximal interphalangeal joints, and
 - o 8 distal interphalangeal joints.

- 2 sternoclavicular joints
- 2 shoulder joints
- 2 wrist joints
- 2 knee joints
- 2 tarsal joints, and
- feet
 - o 10 metatarsophalangeal joints
 - 2 first proximal interphalangeal joints, and
 - 8 proximal interphalangeal joints.

The investigator will identify any joints to be excluded from evaluation at each visit. Replaced, synovectomized, ankylosed, or arthrodesed joints should be excluded from evaluation.

Any joint that has had an intra-articular corticosteroid injection within 4 weeks prior to baseline should be excluded from evaluation during the study. The locations or a listing of these previous procedures should be documented in the participant's source documents or CRF.

The joint count will be assessed by scoring aspects of tenderness on pressure and passive movement of the particular joint. The participant will be asked for pain sensations on these manipulations and watched for spontaneous pain reactions. Any positive response on pressure, movement or both will be translated into a single tender-versus nontender dichotomy.

[figure not shown]

The 28 joints examined and assessed as tender or not tender for TJC and as swollen or not swollen for SJC include 14 joints on each side of the participant's body (Smolen et al. 1995):

- 2 shoulders
- 2 elbows
- 2 wrists
- 10 metacarpophalangeal joints
- 2 interphalangeal joints of the thumb
- 8 proximal interphalangeal joints, and
- 2 knees.

8.2. Safety Assessments

Planned time points for all safety assessments are provided in the SoA.

8.2.1. Physical Examinations

A complete physical examination will include, at a minimum, assessments of these system

- cardiovascular
- respiratory
- gastrointestinal, and
- neurological.

The physical examination will determine if there are symptoms of active TB, including measurement of body temperature and assessment of peripheral lymph nodes.

A complete physical examination may be repeated at the investigator's discretion at any time a participant presents with physical complaints.

Investigators should pay special attention to clinical signs related to previous serious illnesses.

Symptom-directed physical assessments after screening

These assessments are performed based on participant status and standard of care.

8.2.2. Vital Signs

For each participant, conduct vital signs measurements according to the SoA (Section 1.3).

Measure vital signs after the participant has been sitting at least 5 minutes, and before obtaining an ECG tracing, or collection of blood samples for laboratory testing.

8.2.3. Electrocardiograms

For each participant, a single 12-lead digital ECG will be collected according to the SoA. The ECG should be recorded before collecting any blood. Participants must be supine for approximately 5 to 10 minutes before ECG collection and remain supine but awake during ECG collection.

ECGs may be obtained at additional times, when deemed clinically necessary. Collection of additional ECGs at a particular time point is allowed to ensure high quality records.

ECGs will be interpreted by a qualified physician (the investigator or qualified designee) at the study site as soon after the time of ECG collection as possible, and ideally while the participant is still present, to determine whether the participant meets the study entry criteria and for immediate participant management, should any clinically relevant findings be identified.

If a clinically significant finding is identified after enrollment, the investigator in conjunction with the sponsor will determine if the participant can continue in the study and if any change in participant management is needed.

8.2.4. Clinical Safety Laboratory Tests

See Section 10.2, Appendix 2 for the list of clinical laboratory tests to be performed and the SoA for the timing and frequency.

The investigator must review the laboratory results, document this review, and report any clinically relevant changes occurring during the study as an AE. The laboratory results must be retained with source documents unless a Source Document Agreement or comparable document cites an electronic location that accommodates the expected retention duration.

Clinically significant abnormal laboratory findings are those which are not associated with the underlying disease, unless judged by the investigator to be more severe than expected for the participant's condition.

All laboratory tests with values considered clinically significantly abnormal during participation in the study or within approximately 50 days after the last dose of study intervention should be repeated until the values return to normal or baseline or are no longer considered clinically significant by the investigator or medical monitor.

- If such values do not return to normal/baseline within a period of time judged reasonable by the investigator, the etiology should be identified and the sponsor notified.
- All protocol-required laboratory assessments, as defined in Section 10.2, Appendix 2, must be conducted in accordance with the SoA, standard collection requirements, and laboratory manual.

If laboratory values from non-protocol specified laboratory assessments performed at an investigator-designated local laboratory require a change in participant management or are considered clinically significant by the investigator, for example, SAE or AE or dose modification, then report the information as an AE.

8.2.5. Pregnancy Testing

Pregnancy testing will occur as outlined in the SoA.

Details of all pregnancies in female participants and, if indicated, female partners of male participants will be collected as outlined in Sections 8.3.1 and 8.3.2.

8.2.6. Suicidal Ideation and Behavior Risk Monitoring

Participants should be monitored appropriately and observed closely for suicidal ideation and behavior or any other unusual changes in behavior. Participants who experience signs of suicidal ideation and behavior should undergo a risk assessment. All factors contributing to suicidal

ideation and behavior should be evaluated and consideration should be given to discontinuation of the study intervention.

Baseline assessment of suicidal ideation and behavior and intervention emergent suicidal ideation and behavior will be monitored during the study using the C-SSRS.

C-SSRS

The C-SSRS is a scale that captures the occurrence, severity, and frequency of suicidal ideation and behavior during the assessment period via a questionnaire. The scale was developed by the National Institute of Mental Health trial group (TASA) for the purpose of being counterpart to the Columbia Classification Algorithm of Suicide Assessment (C-CASA) categorization of suicidal events.

For this study, the C-SSRS is adapted for the assessment of the ideation and behavior categories only. The Intensity of Ideation and Lethality of Behavior sections are removed.

Nonleading AE collection should occur prior to the collection of the C-SSRS.

If a suicide-related event is discovered *during the C-SSRS* but was not captured during the nonleading AE collection, sites should not change the AE form, except if a serious AE occurs or an AE leading to discontinuation occurs.

If a serious AE occurs, then capture the AE on the AE form and follow the process for reporting SAEs.

If an AE leads to discontinuation, then capture the AE on the AE form and record the reason for discontinuation.

8.2.7. Hepatic Monitoring

Close hepatic monitoring

Initiating laboratory and clinical monitoring for abnormal liver laboratory test results

Laboratory tests, including ALT, AST, ALP, TBL, direct bilirubin, gamma-glutamyl transferase, and creatine kinase, should be repeated within 48 to 72 hours to confirm the abnormality and to determine if it is increasing or decreasing, if 1 or more of the conditions in this table occur.

If a participant with baseline results of	Develops the following elevations
ALT or AST <1.5x ULN	ALT or AST ≥3x ULN
ALP <1.5x ULN	ALP ≥2x ULN
TBL <1.5x ULN	TBL ≥2x ULN (except for participants with Gilbert's syndrome)
ALT or AST ≥1.5x ULN	ALT or AST ≥2x baseline
ALP≥1.5x ULN	ALP ≥2x baseline
TBL ≥1.5x ULN	TBL ≥1.5x baseline (except for participants with Gilbert's
	syndrome)

What to do if the abnormal condition persists or worsens

If the abnormality persists or worsens, the investigator, in consultation with the Lilly-designated medical monitor, should initiate clinical and laboratory monitoring, and evaluation for possible

causes of abnormal liver tests. At a minimum, this evaluation should include physical examination and a thorough medical history, including

- symptoms
- recent illnesses, for example, heart failure, systemic infection, hypotension, or seizures
- recent travel
- history of concomitant medications including over-the-counter, herbal and dietary supplements, and
- history of alcohol drinking and other substance abuse.

Frequency of monitoring

Initially, monitoring of symptoms and hepatic biochemical tests should be done 1 to 3 times weekly, based on the participant's clinical condition and hepatic biochemical tests.

Subsequently, the frequency of monitoring may be lowered to once every 1 to 2 weeks, if the participant's clinical condition and lab results stabilize.

Monitoring of ALT, AST, ALP, and TBL should continue until levels normalize or return to approximate baseline levels.

Comprehensive hepatic evaluation

When to perform a comprehensive evaluation

A comprehensive evaluation should be performed to search for possible causes of liver injury if 1 or more of the conditions in this table occur.

If a participant with baseline results of	Develops the following elevations
ALT or AST <1.5x ULN	ALT or AST ≥3x ULN with hepatic signs/symptoms ^a , or ALT or AST ≥5x ULN
ALP <1.5x ULN	ALP≥3x ULN
TBL <1.5x ULN	TBL ≥2x ULN (except for participants with Gilbert's syndrome)
ALT or AST ≥1.5x ULN	ALT or AST ≥2x baseline with hepatic signs/symptoms ^a , or ALT or AST ≥3x baseline
ALP≥1.5x ULN	ALP ≥2x baseline
TBL ≥1.5x ULN	TBL ≥2x baseline (except for participants with Gilbert's syndrome)

^a Hepatic signs or symptoms are severe fatigue, nausea, vomiting, right upper quadrant abdominal pain, fever, rash, and/or eosinophilia >5%.

What a comprehensive evaluation should include

At a minimum, this evaluation should include

- physical examination and a thorough medical history, as outlined above
- tests for
 - o PT-INR
 - o viral hepatitis A, B, C, or E
 - o autoimmune hepatitis, and
- an abdominal imaging study, for example, ultrasound or CT scan.

Based on the participant's history and initial results, further testing should be considered in consultation with the Lilly-designated medical monitor, including tests for

- hepatitis D virus
- cytomegalovirus
- Epstein-Barr virus
- acetaminophen levels
- acetaminophen protein adducts
- urine toxicology screen
- Wilson's disease
- blood alcohol levels
- urinary ethyl glucuronide, and
- blood phosphatidylethanol.

Based on the circumstances and the investigator's assessment of the participant's clinical condition, the investigator should consider referring the participant for a hepatologist or gastroenterologist consultation, magnetic resonance cholangiopancreatography, endoscopic retrograde cholangiopancreatography, cardiac echocardiogram, or a liver biopsy.

Additional hepatic data collection (hepatic safety CRF) in study participants who have abnormal liver tests during the study

Collect additional hepatic safety data in hepatic safety CRFs if a study participant develops a hepatic event considered to be an SAE or discontinues study intervention due to a hepatic event or meets 1 of the conditions described in this table.

If a participant with baseline results of	Develops the following elevations
ALT <1.5x ULN	ALT to $\geq 5x$ ULN on 2 or more consecutive blood tests
ALT ≥1.5x ULN	ALT $\ge 3x$ baseline on 2 or more consecutive blood tests
TBL <1.5x ULN	TBL ≥2x ULN, except for participants with Gilbert's syndrome
TBL≥1.5x ULN	TBL ≥2x baseline
ALP <1.5x ULN	ALP ≥2x ULN on 2 or more consecutive blood tests
ALP ≥1.5x ULN	ALP to $\ge 2x$ baseline on 2 or more consecutive blood tests

Note: the interval between the 2 consecutive blood tests should be at least 2 days.

8.2.8. Tuberculosis Testing and Monitoring

Tuberculosis testing at screening Visit 1

Medical history will determine the lifetime risk factors for TB infection, for TB progression, and for symptoms or signs of active TB.

A physical examination will determine symptoms of active TB, including measurement of body temperature and assessment of peripheral lymph nodes.

A chest x-ray will be interpreted and reported by a radiologist or pulmonologist, as specified in the SoA (Section 1.3). Participants do not need to have a chest x-ray at screening if results from a chest x-ray within 3 months prior to the study are available.

All participants with no history of LTBI or active TB, and no history of positive Mantoux tuberculin skin test (TST) using purified protein derivative (PPD) or positive *Mycobacterium tuberculosis* interferon gamma release assay (IGRA), must have either a PPD, TST or IGRA for *M. tuberculosis*.

PPD TST

An induration of 5 or more millimeters is considered positive in persons

- with HIV-infection
- with a recent contact with a person with TB disease
- with fibrotic changes on chest radiograph consistent with prior TB
- with organ transplants, or
- who are immunosuppressed for other reasons, for example, taking the equivalent of >15 mg/day of prednisone for 1 month or longer, or taking tumor necrosis factor -α antagonists.

An induration of 10 or more millimeters is considered positive in all other potential study participants.

Two-step testing, repeating TST from 1 to 3 weeks after the first TST, is recommended for certain participant groups, including persons

- receiving immunosuppressant treatment
- with a history of temporally remote increased risk of TB infection, or
- for whom the first test is negative, as per local public health or professional medical society recommendations.

IGRA for M. tuberculosis

Ensure that specimen handling, transport, timing, and laboratory procedures meet all requirements per package insert.

Diagnosed LTBI

Participants diagnosed with LTBI are excluded (Section 5.2) unless they are candidates for LTBI treatment, are treated for LTBI, and the following criteria are met:

[figure not shown]
- After receiving at least 4 weeks of LTBI therapy, per the WHO or the United States CDC guidelines, there is no evidence of hepatotoxicity, defined as ALT/AST ≤2 times ULN, or other treatment intolerance.
- The participant completes appropriate LTBI therapy.

Monitoring during the study

At a minimum, each participant will have the following documented at least every 3 months

- thorough history to determine any risk factors for TB infection and for TB progression, symptoms, or signs of active TB, and
- thorough physical examination that includes assessment for signs of active TB, including measurement of body temperature and assessment of peripheral lymph nodes.

8.2.9. Hepatitis B Testing and Monitoring

The following actions should be taken in response to HBV DNA test results during the study.

If	Then
a single result is obtained with a value "below limit of	the test should be repeated within approximately
quantitation"	2 weeks
the repeat test result is "target not detected"	monitoring may resume according to the study
	schedule
the participant has 2 or more test results with a value	HBV DNA testing should be performed approximately
"below limit of quantitation" during the study	once per month for the remainder of the study and
	referral to a hepatologist is recommended
a result is obtained with a value "above limit of	the participant will be permanently discontinued from
quantitation" at any time during the study	the study intervention (see Section 7.1) and should be
	referred to a hepatologist immediately.

Management of enrolled participants with detectable HBV DNA during the study

If HBV DNA is detected, study intervention will be temporarily withheld or permanently discontinued, as described in Sections 7.1 and 7.1.3, and the participant should receive appropriate follow-up medical care.

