7.1.3. Temporary Discontinuation of Study Intervention

Infection-related criteria for temporary discontinuation of study intervention

This table describes the required criteria for temporarily discontinuing study intervention and the next steps the site staff should follow.

If a participant develops	Then follow this guidance
serious or opportunistic infections, as defined in the	Withhold study intervention until resolution of all
exclusion criteria (Section 5.2)	acute clinical signs and symptoms, and completion of
	all appropriate anti-infective treatment.
	The investigator should consult with the sponsor-
	designated medical monitor to determine when it is
	appropriate to restart study intervention.
any acute infection or illness	At the discretion of the investigator and sponsor or its
	designee, withhold intervention until resolution of all
	acute clinical signs and symptoms, and completion of
	all appropriate anti-infective treatment.
positive HBV DNA results	Contact the sponsor-designated medical monitor.
or	Repeat HBV DNA testing as soon as possible.
results detecting HBV DNA, but the HBV DNA is	If HBV DNA is confirmed as positive, then
below the level of quantification	permanently discontinue intervention.
LTBI and the participant is a candidate for LTBI	Withhold study intervention for at least the first 4
treatment	weeks of LTBI treatment.
	If there is no evidence of hepatotoxicity
	(ALT/AST must remain ≤2 times ULN) or other
	treatment intolerance after receiving at least 4
	weeks of appropriate LTBI therapy, per WHO or
	CDC guidelines, then restart study intervention.
	The participant must complete appropriate LTBI
	therapy before restarting study intervention.

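### For a quantifiable HBV DNA result with a negative repeat, Protocol 7.1 and 8.2.9 end study drug, but the HBV row of 7.1.3 ties the permanent stop to confirmation and gives no explicit hold or restart rule

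*Protocol*

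**What the plan says.** Three places in the protocol govern an HBV DNA result during the study.

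- **Section 7.1** lists a positive HBV DNA test among the reasons for permanent discontinuation of study drug. It sets no confirmation condition and refers to 8.2.9 for details. Its additional HBV guidance asks for a physician with viral hepatitis expertise to be involved before discontinuation and to advise on timing relative to antiviral treatment.
- **Section 8.2.9** works by result. After one result above the limit of quantitation, at any time, "the participant will be permanently discontinued from" study drug and should be referred to a hepatologist immediately; no repeat is requested. After a single result below the limit, the test is repeated within about 2 weeks, and scheduled monitoring resumes if the target is not detected. After two or more results below the limit, testing becomes monthly and "referral to a hepatologist is recommended". The section ends: "If HBV DNA is detected, study intervention will be temporarily withheld or permanently discontinued, as described in Sections 7.1 and 7.1.3".
- **Section 7.1.3** has one HBV row with two triggers, "positive HBV DNA results" and "results detecting HBV DNA, but the HBV DNA is" below quantification. The action is the same for both: contact the medical monitor, then "Repeat HBV DNA testing as soon as possible", then "If HBV DNA is confirmed as positive, then" stop permanently.

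**The concern.** A stopping rule for viral hepatitis risk under an immunomodulator should give one answer for one set of results. Here a site or medical monitor working from 8.2.9 ends treatment on the first quantifiable result. One working from the 7.1.3 row waits for the repeat and, if it is negative, finds no trigger for a permanent stop. The same pair of results could end treatment for one participant and leave another in the study on drug.

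The row also leaves dosing unstated while the repeat is pending and after it comes back clear. This matters mostly for results below quantification, where 8.2.9 says when monitoring resumes but not when dosing does.

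**Working it through.** No sample size, power or error-rate figure is involved, so the main check is a comparison of the texts.

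**Step 1: what counts as positive in 7.1.3.** The row names results below quantification as a separate trigger. Its first trigger must therefore cover quantifiable results, which are exactly those that 8.2.9 sends to a permanent stop.

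**Step 2: the result sequences side by side.**

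| First result, then repeat | 7.1 with 8.2.9 | 7.1.3 HBV row |
|---|---|---|
| Above limit, then above limit | Permanent stop on the first result | Permanent stop after the repeat |
| Above limit, then negative | Permanent stop on the first result | Stop condition not met; dosing not addressed |
| Below limit, then target not detected | Scheduled monitoring resumes; dosing not addressed | Stop condition not met; dosing not addressed |
| Below limit, then below limit | Monthly testing, referral recommended; dosing not addressed | Not a positive in the row's own terms; dosing not addressed |

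Only the second sequence gives different final dispositions.

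**Step 3: does other text decide it?** The specialist guidance in 7.1 concerns who is involved and when the stop happens relative to antiviral treatment, not whether an unconfirmed result ends treatment. The closing sentence of 8.2.9 cites 7.1 and 7.1.3 together and ranks neither. Exclusion criterion 22 acts only at entry.

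**Step 4: hold and restart.** The 7.1.3 table has four rows. Those for serious or opportunistic infection, acute infection, and latent tuberculosis all say to withhold, for example "Withhold study intervention until resolution of all" acute signs and symptoms. Each also gives an end-point for the hold or restart conditions. The HBV row has neither. A hold can still be inferred, because the table is introduced as criteria for temporary discontinuation and 8.2.9 says drug is either withheld or stopped when HBV DNA is detected. No restart condition can be inferred from any HBV text.

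**Step 5: size.** The inputs are 420 participants, about 60 in the 100 mg arm and about 120 in each other group (SAP Section 5), and a 60-week treatment period with the primary endpoint at Week 12 (SAP 1.1 and 1.2). The documents give no frequency, so assume that 1 to 4 participants have a quantifiable on-study result and 0% to 50% of these fail to confirm.

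- Participants in the conflicting case: lowest 1 × 0 = 0; highest 4 × 0.5 = 2. As a share, 2/420 = 0.48%.
- Before Week 12, if events are spread evenly: 12/60 = 20%, so at most 2 × 0.20 = 0.4 participants.
- Effect of one reclassified participant on an arm's ACR20 rate: 100/120 = 0.83 points or 100/60 = 1.67 points, and only if that person would otherwise have responded.
- Largest expected shift, with all cases in the 100 mg arm: 0.4 × 100/60 = 0.67 points.

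**The case against.** The best defence is that following all three sections together gives one answer. Section 8.2.9 is the specific section on HBV results, it is mandatory, and 7.1 refers to it for details. Section 7.1.3 deals with temporary discontinuation, and a negative repeat there does not cancel a stop already triggered elsewhere. A site can stop, refer and repeat at once. The 7.1.3 row also sends every such case to the sponsor's medical monitor, and 7.1 brings in a hepatitis specialist, so no site is meant to decide alone.

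Much of this stands. The reading is workable, and the controls limit the risk. What remains is that the 7.1.3 table is presented as required criteria and next steps for site staff, that 8.2.9 itself sends the reader there, and that the row makes confirmation the stated route to a permanent stop for quantifiable results. The medical monitor has no single written rule to apply.

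Three stronger readings are tempting but not supported:

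- A reader might infer that 7.1.3 forbids a permanent stop before confirmation. The row does not say that confirmation is the only route.
- A reader might infer that nothing requires a hold. The table's introduction and the end of 8.2.9 imply one; the row simply does not state it.
- A reader might infer that two results below the limit count as confirmed and so require a permanent stop. The row separates positive results from those below quantification, and 8.2.9 gives repeated low results their own rule.

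**Conclusion.** The inconsistency is real and lies in current, unredacted text. It is confined to a quantifiable result followed by a negative repeat, where 7.1 and 8.2.9 agree and the HBV row of 7.1.3 is the outlier. The second defect is that this row has no explicit withhold instruction and no restart condition.

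Severity is minor. A reader might infer that the primary result is at risk, because permanent discontinuation is an intercurrent event: nonresponse for categorical endpoints, later data excluded for continuous endpoints at Week 12, and last observation carried forward at Weeks 24 and 60 (SAP 1.1). The numbers do not support that. Under the assumed frequencies, 0 to 2 of 420 participants are in the conflicting case, at most 0.4 of them before Week 12, and the expected shift in any arm's ACR20 rate is at most 0.67 points. The reason to act is consistent safety management. The size rests wholly on the assumed frequencies and on even timing over 60 weeks; the textual finding does not.

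**What to change.** Split the 7.1.3 HBV row by result.

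1. **Above the limit of quantitation:** permanent discontinuation and immediate hepatologist referral, as in 7.1 and 8.2.9, with the specialist input already in 7.1. A repeat may be done but does not reverse the stop.
2. **Detected but below the limit:** contact the medical monitor, withhold study drug, repeat within about 2 weeks, and restart if the target is not detected. If a second result is below the limit, follow the existing 8.2.9 rule (monthly testing, hepatologist referral recommended), with dosing decided with the medical monitor.

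Replace the shared confirmation sentence with a statement that any result above the limit falls under (1). Deleting only the condition would leave the permanent stop applying to low-level results as well.

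The cost is a protocol amendment to a safety rule. Under Protocol 10.1.1 it needs ethics approval and, if substantial, health authority approval, so it is best bundled with another amendment.

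Option (2) will sometimes delay a dose. Assume a laboratory turnaround of t days and a repeat 14 days after the first result is reported. The hold then ends t + 14 + t days after the first sample: 20, 28 or 34 days for t = 3, 7 or 10. If that sample is taken 28 days before the next dose, the dose is late by 0, 0 or 6 days. This covers Q4W dosing sampled on a dosing day. Q12W dosing has 84 days of room if sampled on a dosing day, but less if sampled later in the interval; the visit schedule is not visible in the public protocol.
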